### **5.5.3 Demographic and Other Baseline Characteristics**

Subject demographic (age, sex, race, and ethnicity) and Baseline characteristics will be summarized for the Safety and PK populations. Age will be represented as both a continuous and as a categorical variable.

#### **5.5.3.1 Concomitant Medications**

Concomitant medications will be coded using the World Health Organization Drug Dictionary Enhanced. All medications will be presented in the data listings. A table of concomitant medications by percentage of subjects who used them will also be provided. No statistical tests will be performed.

#### **5.5.4 Measurements of Treatment Compliance**

No formal evaluations of compliance are planned.

#### **5.5.5 Analysis of Efficacy**

Efficacy assessments will be summarized at Baseline, Week 24 and Week 52.

The primary efficacy endpoint for this study is the complete cure rate of the TGT at Week 52. Complete cure is defined as 0% clinical involvement of the TGT and negative mycology (negative KOH wet mount and negative fungal culture) at Week 52.

The secondary efficacy endpoints include the following:

- Complete or almost complete cure of the TGT at Weeks 24 and 52
- Treatment success (Clinical Efficacy rate) of the TGT at Weeks 24 and 52 defined as completely Clear Nail (CN) or almost CN
- Negative mycology (Mycological Cure rate) of the TGT at Weeks 24 and 52 defined as negative KOH wet mount and negative fungal culture
- Negative fungal culture of the TGT at Weeks 24 and 52

The primary and secondary efficacy endpoints will be summarized for the safety population with descriptive statistics including sample size, frequency count, and percentage.

**5.5.6 Statistical/Analytical Issues****5.5.6.1 Adjustments for Covariates**

No planned analyses include covariates.

**5.5.6.2 Handling of Dropouts or Missing Data**

No imputations will be made for missing data.

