### **5.3 Treatments**

KERYDIN (tavaborole) topical solution, 5% will be applied topically once daily for 48 weeks.

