### 5.4.3.3      **Clinical Safety Laboratory Parameters and Pregnancy Tests**

Clinical safety laboratory parameters will be assessed at Baseline, Week 24, and Week 52/ET, if applicable. Laboratory tests may be repeated more often if clinically indicated. Blood samples may be taken with the subject in a non-fasting state.

All out-of-normal range laboratory values must be evaluated by the Investigator or subinvestigator as to whether they are clinically significant (i.e., require medical intervention or have clinical signs and/or symptoms). Abnormal clinical laboratory parameters that are considered clinically significant by the Investigator will be recorded on the AE CRF except Baseline visit. Clinically significant laboratory abnormalities noted from the Baseline visit will be recorded as medical history. The AE should be reported as a clinical diagnosis when possible. Laboratory tests will be performed by the central laboratory and are presented in Table 5.

UPTs will be performed at each scheduled visit on postmenarchal females starting at Baseline. If a UPT result is positive, the subject must be discontinued.

The Sponsor will designate a central laboratory for safety laboratory tests. All samples for clinical laboratory tests must be managed through the central laboratory designated by the Sponsor. Sample management (collection, storage, shipping, etc.) will be done according to the central laboratory instructions.

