#### **5.5.2 Data Sets Analyzed**

The following populations will be used:

- **Safety population:** all subjects who receive at least one confirmed dose of study drug and have at least one post-baseline safety assessment.

- **PK population:** all subjects from the maximal use subgroup with available PK data at Day 15 and at least one collection on Day 29.

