### **5.5.8 Safety Analyses**

No imputation will be made for missing safety data.

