### **5.5.8.3 Local Skin Reactions**

LTRs (burning/stinging, induration/edema, oozing and crusting, pruritus, erythema, and scaling) will be evaluated by frequency tables for Baseline and Weeks 2, 4, 8, 16, 24, 32, 40, 48, and 52. Additionally, LTRs as well as change from baseline in LTRs will be summarized by descriptive statistics (mean, standard deviation, median, and minimum and maximum).

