### **5.5.8.4 Safety Laboratory Values**

Laboratory values as well as changes from Baseline in laboratory values will be summarized with descriptive statistics at Baseline, Week 24 and Week 52. In addition, shift tables will be created according to normal ranges. The last laboratory evaluation before the first dose of study drug will be used as Baseline for all laboratory analyses.

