### **5.5.8.5 Vital Sign Measurements**

Vital signs will be summarized with descriptive statistics at Baseline and Weeks 2, 4, 8, 16, 24, 32, 40, 48, and 52. Change from Baseline in vital signs will be summarized at Weeks 2, 4, 8, 16, 24, 32, 40, 48, and 52

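### Does the SAP need a rule on whether early-termination assessments are tabulated under Week 52?

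*SAP*

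**What the plan says.** On collection, Section 5.4.3.3 states: "Clinical safety laboratory parameters will be assessed at Baseline, Week 24, and Week 52/ET, if applicable". Sections 5.1, 5.4.1.1 and 5.4.1.2 use the same combined label for nail severity and mycology. The schedule in Section 5.1.1 heads its last column as Visit 11 or ET, with Study Week 52 beneath it, and marks labs, local tolerability reactions (LTRs) and vital signs there.

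On analysis, only scheduled weeks are named. For labs (Section 5.5.8.4): "Laboratory values as well as changes from Baseline in laboratory values will be summarized with descriptive statistics at Baseline, Week 24 and Week 52". For LTRs (Section 5.5.8.3), these "will be evaluated by frequency tables for Baseline and Weeks 2, 4, 8, 16, 24, 32, 40, 48, and 52". For vital signs (Section 5.5.8.5): "Change from Baseline in vital signs will be summarized at Weeks 2, 4, 8, 16, 24, 32, 40, 48, and 52". Section 5.5.5 does the same for efficacy. None of the by-visit shells has an ET or last-value column.

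On missing data, Section 5.5.6.2 consists of one sentence: "No imputations will be made for missing data". Section 5.5.8 adds "No imputation will be made for missing safety data".

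**The concern.** The primary objective is safety and tolerability, and subjects who leave early are where intolerance may show. Two readings of the SAP look possible, and each seems to have a cost.

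- **ET kept out of Week 52.** An early terminator's last lab values and LTR grades would enter no by-visit table. If the mid-study draw is at Week 24, a subject leaving before then would have no post-baseline lab in any table. A subject leaving before Week 2 might join the Safety population, whose members must "have at least one post-baseline safety assessment", through the ET visit alone, and then contribute nothing to the post-baseline columns.
- **ET counted as Week 52.** Section 5.3 says "KERYDIN (tavaborole) topical solution, 5% will be applied topically once daily for 48 weeks", so Week 52 falls 52 − 48 = 4 weeks after planned treatment ends. ET values taken closer to treatment could be pooled with off-treatment follow-up.

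The rule touches the Week 52 results of 10 + 11 = 21 lab tests, 6 LTR signs, 4 vital signs and 1 + 4 = 5 of the 1 + 4 × 2 = 9 efficacy summaries.

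**Working it through.** **1. Collection against tabulation.**

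| Data | Collected | Tabulated |
|---|---|---|
| Labs (5.4.3.3; 5.5.8.4) | Baseline, Week 24, Week 52/ET | Baseline, Week 24, Week 52 |
| LTRs (5.4.3.1, 5.1.1; 5.5.8.3) | Baseline and each later visit, the last being Visit 11 or ET | Baseline and nine weeks up to 52 |
| Vital signs (5.4.3.2, 5.1.1; 5.5.8.5) | Each visit, the last being Visit 11 or ET | Baseline and nine weeks up to 52 |
| Nail severity, mycology (5.4.1.1, 5.4.1.2; 5.5.5) | Screening, Week 24, Week 52/ET | Baseline, Week 24, Week 52 |

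No sentence links the ET part of the middle column to the right-hand column, so the gap is confirmed.

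**2. What an analyst would do.** ET shares a visit number and a study-week column with Week 52. The last row of the table also shows how the SAP uses its labels: nail severity and mycology are collected at Screening, yet Section 5.5.5 and Table 14.2.1 report them under Baseline. Column labels thus work as collection slots. On that convention the Week 52 column is the Visit 11 or ET slot.

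**3. How far the readings can differ.** There is no figure in the plan to reproduce: Section 5.5.9 gives no power calculation and no total N, and no dropout rate is stated. The inputs below are assumptions, apart from N = 40, which borrows the minimum number aged 12 to 16 years 11 months. Every terminator is taken to attend an ET visit.

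Take 8 ET subjects, 32 completers with 1 event, and ET event rate r:

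- Without ET: 1/32 = 3.1%.
- With ET: (1 + 8r)/40, which is 2.5% for r = 0, 3.1% for r = 1/32, 7.5% for r = 0.25 and 12.5% for r = 0.5.

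Now vary dropout, with 1 completer event and r = 0.25:

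| Dropout | ET | Without ET | With ET |
|---|---|---|---|
| 10% | 4 | 1/36 = 2.8% | 2/40 = 5.0% |
| 20% | 8 | 1/32 = 3.1% | 3/40 = 7.5% |
| 30% | 12 | 1/28 = 3.6% | 4/40 = 10.0% |

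The difference is the dropout fraction times the gap between the ET and completer rates. At 20% dropout and r = 0.25 it is 0.20 × (25 − 3.1) = 4.4 percentage points. This shows that pooling unlike groups moves a percentage. It does not show that the groups are unlike here.

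**4. What would be lost if ET were left out.**

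- LTRs needing treatment, interruption or discontinuation are also recorded as adverse events (Section 5.4.3.1).
- Clinically significant post-baseline labs are recorded as adverse events (Section 5.4.3.3).
- Events leading to withdrawal have Table 14.3.1.2.2 and Listing 16.2.7.2.5.
- Scheduled visits attended before ET stay in their own columns.
- All LTR grades and lab values are in Listings 16.2.7.1 and 16.2.8.2.1, and abnormal labs also in Listing 16.2.8.2.2.

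That leaves untreated LTR grades, lab shifts judged not clinically significant, and the ET visit's share of the lab and vital-sign means, all from one visit per early terminator. These would be missing from the tables but not from the report.

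**5. Two of the costs are weaker than they look.** The SAP does not say when an ET visit falls relative to the last dose, and the title of Table 14.3.1.2.2 treats stopping study drug and leaving the study as separable. The mixing of on- and off-treatment values therefore cannot be shown. Also, the schedule as it reads in the available text marks the mid-study lab draw under Visit 6 (Week 16), while Sections 5.1 and 5.4.3.3 say Week 24. This may come from how the table was read. If it is real, a subject leaving between those weeks would already have a post-baseline draw.

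**The case for a change.** The strongest case for a change is that a visit schedule governs collection, not analysis. The same schedule allows ±7 days around Visits 4 to 11, and an ET visit at, say, Week 10 is far outside any Week 52 window. Assigning data to table columns is the SAP's job, two programmers could produce different tables from this text, and one sentence would prevent that at no cost in data.

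The part that stands is that the rule is unwritten. The part that does not is the claim that the result would be unsound. Either assignment is acceptable. Each by-visit cell carries its own N, which can be set against the number of completers in Table 14.1.1.1, so a reader can largely see whether ET subjects were counted. A separate ET column would hold few subjects at scattered study days, and it could not be relied on to separate on-treatment from off-treatment values. For efficacy, Section 5.4.1 describes the assessments as a check on compliance, so the effect there is minor.

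**Conclusion.** No change to the plan is called for. The SAP leaves a detail unwritten that its own visit schedule lets analysts fill sensibly, by treating Visit 11 or ET as the Week 52 slot. The no-imputation rule is sound and is not affected.

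The size cannot be derived from the SAP. The illustrated range of 2.5% to 12.5% against 3.1% rests wholly on assumed dropout, full ET attendance and assumed event rates, and it vanishes when ET subjects and completers have the same rate. The conclusion rests on three features of the plan: the analysis is descriptive with one arm, the clinically important findings of early terminators reach the adverse event tables, and the listings retain every ET value. A table footnote giving the number of ET subjects and their range of study days would be a courtesy to the reader. It belongs to programming and does not correct an error.

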**5.5.6.3 Interim Analyses and Data Monitoring**

No interim analyses are planned.

**5.5.6.4 Multicenter Studies**

The study will be conducted at multiple investigational centers with the intention of pooling the results for analysis.

**5.5.6.5 Multiple Comparisons/Multiplicity**

Not applicable.

**5.5.6.6 Use of an “Efficacy Subset” of Patients**

Not applicable.

**5.5.6.7 Active-Control Studies Intended to Show Equivalence**

Not applicable.

**5.5.6.8 Examination of Subgroups**

No subgroup summaries are planned.

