### 5. INVESTIGATIONAL PLAN

#### 5.1 Overall Study Design

This is an open-label study to evaluate the safety, tolerability, and pharmacokinetics of KERYDIN (tavaborole) topical solution, 5% in treating distal subungal onychomycosis (DSO) of the toenail in pediatric subjects ages 6 to 16 years and 11 months. An eligible subject will have a target great toenail (TGT) with at least 20% involvement with a positive potassium hydroxide (KOH) wet mount and positive fungal culture for *T. rubrum* or *T. mentagrophytes* from a sample obtained from an affected great toenail during the Screening period. KOH and fungal culture will be sent to a central mycology laboratory for eligibility determination. Both great toenails can be sampled at Screening.

The mycological confirmation of eligibility will be performed as follows:

1. Initial sample is KOH (+) and culture (+) for *T. rubrum* or *T. mentagrophytes*, with or without co-infection with *Candida* spp. or *E. floccosum*, subject is eligible for enrollment within the maximum period of 10 weeks (i.e., within 70 days) from the Screening visit.
2. Initial sample is KOH (−) or initial sample is KOH (+) and culture (−): The sample may be repeated and will be assessed as follows:
  - If a repeat sample is KOH (+) and culture (+) for *T. rubrum* or *T. mentagrophytes* with or without co-infection with *Candida* spp. or *E. floccosum*, for enrollment as long as the subject is enrolled within the maximum period of 10 weeks (i.e., within 70 days) from the Screening visit.

Eligible subjects will apply KERYDIN (tavaborole) topical solution, 5% once daily to all affected toenails (the TGT as well as all other toenails identified by the Investigator at the Baseline visit as having the clinical characteristics of onychomycosis) throughout the 48-week treatment period.

Subjects will be evaluated at Screening, Baseline (Day 1), and at Weeks 2, 4, 8, 16, 24, 32, 40, 48, and 52. Each evaluation will include a clinical assessment of the adverse events (AEs) and local tolerability evaluation.

Additional procedures are performed as follows:

- Mycology sampling at Screening, Week 24, and Week 52/early termination (ET)
- Clinical disease severity of the TGT at Screening, Week 24, and Week 52/ET
- Safety laboratory testing at Baseline, Week 24, and Week 52/ET
- Digital photography at Screening, Week 24, and Week 52/ET

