- Urine pregnancy tests (UPTs) will be performed on all postmenarchal females at all scheduled visits starting at the Baseline visit.

Subjects will start diaries at Baseline (Day 1) and will complete the diary as instructed.

In this study, there will be a PK subgroup of at least 16 evaluable subjects ages 12 to 16 years and 11 months studied under maximal use conditions. Subjects in this maximal use subgroup will apply the study drug on all 10 toenails, including up to 2 mm of the surrounding skin, for 28 days ( $\pm$ 7 days). On Day 15, a pre-dose PK sample will be collected to assess steady state trough level. On Day 29, the study drug application will be done at the study site, and PK samples will be collected prior to dosing, as well as 4, 6, 8, and 24 hours post-dose on Days 29-30. After PK sampling is complete, study drug will be applied only to the affected toenails.

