### **5.5.9 Determination of Sample Size**

The study will enroll subjects ages 6 to 16 years and 11 months with at least 40 subjects ages 12 to 16 years and 11 months. All subjects will be assigned to receive active treatment with KERYDIN (tavaborole) topical solution, 5%. A PK subgroup of at least 16 evaluable subjects ages 12 to 16 years and 11 months will be studied under maximal use conditions.

The sample size is considered adequate to achieve the study objectives. No formal power calculations were performed.

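### The Week 2 and Week 4 tolerability summaries pool two treated areas, and a Week 4 to Week 8 change cannot be separated from the planned cut in area

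*SAP*

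**What the plan says.** Section 5.1 of the SAP sets up two application schemes that run side by side. Eligible subjects in general apply the drug "once daily to all affected toenails". The PK subgroup does something different at first: "Subjects in this maximal use subgroup will apply the study drug on all 10 toenails, including up to 2 mm of the surrounding skin". This lasts 28 (±7) days, and then the scheme changes: "After PK sampling is complete, study drug will be applied only to the affected toenails". Section 5.5.9 gives the sizes: "A PK subgroup of at least 16 evaluable subjects ages 12 to 16 years and 11 months will be studied under maximal use conditions", and enrolment "with at least 40 subjects ages 12 to 16 years and 11 months". It states no overall total and no number for children aged 6 to 11.

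On analysis, section 5.5.6.8 says: "No subgroup summaries are planned". Section 5.5.8.3 says that LTRs "will be evaluated by frequency tables for Baseline and Weeks 2, 4, 8, 16, 24, 32, 40, 48, and 52", with means and changes from Baseline as well. In section 6, the shells for LTRs, adverse events, laboratory values, vital signs and extent of exposure all use the Safety population with a single KERYDIN column. PK-population tables cover only demographics, baseline characteristics, concentrations and PK parameters. In the summary tables the maximal-use subgroup itself appears only in Table 14.1.1.1.1, as a head count and as a reason for exclusion from the PK population.

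**The concern.** Safety and tolerability are the primary objective (section 4), and maximal use is the highest exposure in the trial. Two of the scheduled post-baseline LTR assessments, Weeks 2 and 4, fall within the maximal-use period. The next, at Week 8, comes after the switch. A pooled Week 2 or Week 4 rate therefore describes neither scheme. A reader who compares Week 4 with Week 8 sees any real change in tolerability together with a planned reduction in treated area.

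The LTR tables matter more than usual here. Section 5.4.3.1 keeps reactions off the adverse event form unless they need treatment, interruption or discontinuation. For most local reactions the LTR tables are thus the only summary.

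**Working it through.** The SAP states no power or precision figure, so there is none of its own to reproduce. The check has a reading part and an illustrative part.

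**Reading the shells.** Each safety and exposure shell in section 6 was checked for a split by maximal use. None has one.

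**Share of the subgroup.** Share s = 16/N. Sixteen is the stated minimum of evaluable subjects. N is not stated, so it is assumed. Forty is the floor for adolescents alone.

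- N = 40: 16/40 = 40%
- N = 60: 16/60 = 27%
- N = 80: 16/80 = 20%

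**Effect on pooled LTR rates.** Pooled rate = s × p_max + (1 − s) × p_rest. The rates p_max = 25% and p_rest = 10% are assumptions. Each group's rate under a given scheme is held constant over time, so no adaptation occurs, and after the switch everyone is at 10%.

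| N | Pooled rate, Weeks 2 and 4 | Week 8 | Apparent fall |
|---|---|---|---|
| 40 | 0.40 × 25 + 0.60 × 10 = 16% | 10% | 6 points |
| 60 | 0.267 × 25 + 0.733 × 10 = 14% | 10% | 4 points |
| 80 | 0.20 × 25 + 0.80 × 10 = 13% | 10% | 3 points |

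**Effect on exposure.** Treatment lasts 48 × 7 = 336 days, of which 28 are at maximal use (8%; 6% to 10% over 21 to 35 days). The number of affected nails is assumed. For one maximal-use subject:

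- 2 affected nails: 28 × 10 + 308 × 2 = 896 nail-applications, against 336 × 2 = 672, or +33%.
- 4 affected nails: 28 × 10 + 308 × 4 = 1512, against 336 × 4 = 1344, or +12.5%.

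In the pooled mean these shrink with the share. At 40% they become about 13% and 5%; at 20%, about 7% and 2.5%. Table 14.4.1 does not count nail-applications. It reports dosing days, applications and grams, and of these treated area clearly affects only the grams.

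**Precision of a separate column.** With 0 events in n subjects, the one-sided 95% upper bound is 1 − 0.05^(1/n). For n = 16 it is 17.1%. The chance of seeing at least one event in 16 is 56%, 81% or 97% at true rates of 5%, 10% or 20%.

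**The case against.** The strongest reply is that section 4 gives the subgroup a PK purpose only. The SAP does not promise a maximal-use safety result and then fail to deliver it. It also plans no test of trend and no Week 4 to Week 8 comparison, only by-visit descriptions. If the larger area provokes more reactions, pooling raises the early overall rates rather than flattering the drug. All of this is fair, and it limits the weight of the point. It does not remove the mixing, because subgroup subjects enter the tables for the primary objective and by-visit tables invite reading across visits.

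Several stronger readings are tempting, and the SAP does not support them.

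- A reader might infer that the maximal-use safety result is lost. It is not: section 7 plans by-subject listings of analysis populations (16.2.3), LTRs (16.2.7.1) and treatment-emergent events (16.2.7.2.3), and section 5.5.8.2 has event onset shown in days from first administration. What is missing is a summary.
- A reader might take 40% as the subgroup's share, or as its ceiling. It is neither. Children aged 6 to 11 and further adolescents would lower it, and 16 is itself a minimum.
- A reader might apply the 33% or 12.5% to the pooled exposure table. Those figures are per maximal-use subject.
- A reader might treat a simple contrast of the subgroup with everyone else as clean. It would not be: the subgroup is adolescent only, and a subject outside it with many affected nails comes close to the same treated area.

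**Conclusion.** The point holds as a cheap improvement. If section 5.5.6.8 is followed as written, the Week 2 and Week 4 LTR summaries and the early adverse events mix two exposures, no summary shows tolerability under the highest one, and a pooled Week 4 to Week 8 change cannot be separated from the planned reduction in treated area. These conclusions follow from the text and the shells alone.

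The size does not. An apparent fall of 3 to 6 points rests on assumed totals of 80 down to 40 and on assumed rates of 25% and 10%. The SAP does not show that reactions are in fact more frequent under maximal use.

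**What to change.** Replace the sentence in section 5.5.6.8 with a planned descriptive split and no tests. Define it by membership of the maximal-use subgroup. The PK population is unsuitable, because section 5.5.2 requires Day 15 data and at least one Day 29 collection. Someone who stopped early, perhaps for intolerance, would be left out.

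Use four columns: maximal-use subjects; other subjects aged 12 to 16 years 11 months; subjects aged 6 to 11; and total. Apply them to:

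- Tables 14.3.1.1.1 and 14.3.1.1.2 at Weeks 2, 4 and 8;
- treatment-emergent adverse events with onset up to one study-day cut-off common to all subjects, for example Day 30 or the Week 4 visit (the end of PK sampling will not serve, since most subjects have none);
- grams applied in Table 14.4.1.

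Add a footnote that maximal-use subjects change treated area after PK sampling, so that Week 4 to Week 8 changes in their column and in the total reflect that change.

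The cost is SAP wording and extra columns. Subgroup membership is already counted in Table 14.1.1.1.1, and the age bands already stand in Table 14.1.2.1. The drawback is a column of about 16 subjects, where zero events still leaves an upper bound of about 17%. That is acceptable for description if stated.
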